8.3.1. Incidental Gluten Exposure Assessment

Incidental gluten exposure will be assessed daily as part of the participant's eDiary. Assessment of any incidental gluten exposure will be reviewed at all study visits.

8.3.2. Vital Signs

Any untoward vital sign findings that are identified during the active collection period and meet the definition of an AE or SAE ([Appendix 3](#)) must be reported according to the processes in [Sections 8.4.1](#) to [8.4.3](#).

Vital signs will be monitored during and after study intervention infusions to assess for IRR (see [Appendix 9](#)). Vital signs will be taken before collection of laboratory tests. Height and weight will also be measured and recorded at screening only and captured on the CRF.

BP and PR assessment consists of a single measure of BP and a single PR. Sitting BP and PR measurement will be assessed with a completely automated device.

Manual techniques will be used only if an automated device is not available. BP and PR measurement should be preceded by at least 5 minutes of rest with the participant in a sitting position, in a quiet setting without distractions.

In amendment 3, Part C orthostatic vital signs including SBP, DBP, and PR will be collected as follows:

- Approximately 5 minutes pre-dose;
- Approximately 45 minutes, 2 hours, and then, every 2 hours until discharge, post dose.

Additionally, if a participant experiences treatment-emergent clinically significant orthostatic hypotension or syncope, then, in addition to supportive care, orthostatic vital signs including

DBP, SBP, and PR will be collected every 2 hours, until discharge. **Note:** if planned assessments (pre-dose and 45 min, 2 hr and 4 hour post-dose) overlap unplanned assessments, orthostatic vital signs will be measured only once, not twice at that time.

Measurement of orthostatic vital signs (SBP, DBP, and PR) will occur after:

1. participant has rested in supine position for 5 minutes
2. participant is in standing position for 1 min
3. Participant is in standing position for 3 minutes

Note: Clinically significant orthostatic hypotension (OH) is defined by a fall in systolic blood pressure over 20 mmHg or a fall of in diastolic pressure over 10 mm Hg within 3 minutes of standing. An increase in heart rate of over 30 bpm suggests postural tachycardia syndrome.(Freeman et al, 2011) In case of above, a Grade 3 AE will be documented.

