2.2.3. Clinical Overview

KAN-101 was evaluated in a FIH Phase 1 study in patients with CeD on a GFD (KAN-101-01). This was a 2-part, multicenter study designed to examine the safety and tolerability of SAD (Part A) and MAD (Part B) of KAN-101. A total of 41 participants received at least 1 dose of KAN-101 (0.15 mg/kg, 0.3 mg/kg, 0.6 mg/kg, 1.2 mg/kg, and 1.5 mg/kg) during the study.

In Study KAN-101-01 administration of KAN-101 was effective at inducing T-cell tolerance:

- Three doses of KAN-101, administered 3 days apart, at 0.15, 0.3 and 0.6 mg/kg dose levels was effective in inducing T cell tolerance to gliadin. KAN-101 treated patients exhibited minimal change or a decrease in the gliadin-specific T-cell response following GC while placebo patients exhibited an increase in the gliadin-specific T-cell response following GC.
- KAN-101 also modified the immediate immune reaction upon ingestion of gluten by CeD patients in a dose-dependent manner. Patients treated with 3 doses of 0.6 mg/kg KAN-101, administered 3 days apart, exhibited lower median plasma IL-2 levels

within hours of GC compared to placebo or 0.15 and 0.3 mg/kg KAN-101 dose levels.

KAN-101 demonstrated an acceptable safety and tolerability profile after single and multiple doses at all dose levels tested in the KAN-101-01 study. There were no deaths, SAEs, Grade 3 TEAEs, or DLTs observed. TEAEs were consistent with CeD patients upon gluten ingestion (ie, nausea, emesis, abdominal pain, headache, and diarrhea). No clinically relevant trends were observed for changes in vital signs, physical examination, laboratory tests, or ECG results. There were no meaningful correlations between the frequency of TEAEs and study drug dose level. There was an increased frequency of subjects who experienced GI AEs in the total drug-treated group than in the placebo group. No MTD of KAN-101 was identified in KAN-101-01 and no meaningful safety differences were observed among treatment groups during the study.

Preliminary data from the KAN-101-01 study suggests rapid elimination with mean half-life ranging from 3.74 to 36.8 minutes across 0.15 mg/kg to 1.2 mg/kg doses, following single or repeat IV infusions of KAN-101. The mean KAN-101 maximum exposure (C_{max}) and systemic exposure (AUC) appeared to exhibit approximate dose proportionality across 0.15 to 1.2 mg/kg dose range. With repeat dosing, there was no accumulation of KAN-101 which was in concordance with the rapid elimination.

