8.3. Safety Assessments

Safety will be assessed through the monitoring of AEs, clinical signs and symptoms, vital signs and clinical laboratory evaluations.

All participants will be monitored continuously for AEs from screening until the safety follow-up visit on Week 52. AE severity will be assessed using the NCI CTCAE v5.0 or higher (see [Appendix 10](#)). The DSMB will review all SAEs and \geq Grade 3 AEs that are assessed to be related to study drug as these events may occur. Any Grade 4 AEs assessed as related to study drug will result in notification of the FDA in parallel with the DSMB.

Participants will be monitored in the clinic for 4 hours following IV study drug administration for IRR (see [Appendix 9](#)).

For Part A, the DSMB will review cumulative safety data by dose cohort before opening a higher dose cohort. DLTs are defined in [Section 4.1.1.1.1](#). Any DLT experienced during the Treatment period (Day 1 to Day 7) through Day 15 prior to GC will result in a pause in the study enrollment and a review of all available safety data by the DSMB prior to dosing any additional participants; further details for cohort stopping rules are presented in [Section 6.6.1.1](#).

In relation to participant safety during the COVID-19 pandemic, current national laws and local recommendations should be strictly adhered to during the study.

Planned time points for all safety assessments are provided in the [SoA](#). Unscheduled safety measurements may be obtained at any time during the study to assess any perceived safety issues.

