3.5.3. Vital Signs

Vital signs will be assessed at Screening, Days 1, 4, 7, 15, 28, Weeks 12, 24, 36, 52, or ET visit. On dosing days, orthostatic vital signs including SBP, DBP, and PR will be collected approximately 5 minutes pre-dose, and approximately 45 minutes, 2 hours, and then, every 2 hours until discharge, post dose.

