6.6.1. Adverse Events

Adverse events will be summarized for SAS according to Sponsor's reporting standards for

- TEAEs
- Serious AEs (SAEs)

TEAEs will be summarized by the number of participants reporting any TEAE, system organ class (SOC), preferred term (PT), severity, relationship to investigational product.

CTCAE is used to grade the severity of AEs. TEAEs related to GC and infusion-related reactions (IRR) will also be summarized separately.

SAEs will be summarized by SOC and PT, and individual SAEs will be listed by participant.

A list of subjects who prematurely discontinue from the study due to an AE will be provided as well.

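### Part C orthostatic checks after 4 h depend on length of stay, and the SAP plans no by-arm comparison limited to the readings every participant shares

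*Protocol*

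**What the plan says.** Protocol 8.3.2 schedules Part C orthostatic blood pressure and pulse before each dose and then at "Approximately 45 minutes, 2 hours, and then, every 2 hours until discharge, post dose". The Part C Schedule of Activities and SAP Part C 3.5.3 ("approximately 45 minutes, 2 hours, and then, every 2 hours until discharge, post dose") repeat the open-ended series.

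Two passages set the part common to everyone. Protocol 8.3 states: "Participants will be monitored in the clinic for 4 hours following IV study drug administration for IRR". The note in 8.3.2 on overlapping readings refers to "planned assessments (pre-dose and 45 min, 2 hr and 4 hour post-dose) overlap unplanned assessments", so the planned set runs to 4 h. After clinically significant orthostatic hypotension or syncope, "DBP, SBP, and PR will be collected every 2 hours, until discharge".

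Protocol 8.3.2 defines clinically significant orthostatic hypotension as a systolic fall over 20 mmHg or a diastolic fall over 10 mmHg within 3 minutes of standing, and adds: "In case of above, a Grade 3 AE will be documented".

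On analysis, SAP Part C 6.6.1 states: "TEAEs will be summarized by the number of participants reporting any TEAE, system organ class (SOC), preferred term (PT), severity". Protocol 9.3.3 also calls for the number of TEAEs. SAP Part C 6.6.3 leaves vital signs to sponsor standards. The vital-sign windows in SAP Part C Appendix 2.1, Table 4, target pre-dose readings on Days 4 and 7 and resume the next day, so post-dose readings on those two days have no window.

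**The concern.** A participant kept past 4 h for nausea, vomiting or an infusion reaction is tested again at 6 h, 8 h and so on; one who leaves at 4 h is not. Each extra test is another chance to become a Grade 3 case. Appendix 9 of the protocol ties continued monitoring to resolution or stability of an infusion reaction, so the longest stays belong to those who reacted. On the first-in-human study, Protocol 2.2.3 reports: "There was an increased frequency of subjects who experienced GI AEs in the total drug-treated group than in the placebo group". If that imbalance recurs and lengthens stays, the KAN-101 arms would be tested more often than placebo.

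TEAE incidence and severity is a secondary endpoint. Protocol 4.2 says the added Part C assessments are meant to give insight into events just after dosing, following the closure of Part B over the frequency and severity of post-dose AEs. Under Protocol 6.6.1.1, related Grade 3 events in the treatment period prompt unblinded DSMB review. The planned by-arm tables would not show whether an excess of orthostatic events came from the drug or from more readings.

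**Working it through.** **The plan's own figures.** The documents give no orthostatic crossing rate, length of stay beyond 4 h, or share kept late. The one design calculation is IL-2 power: difference 2.37, SD 1.53, 26 per group, two-sided 5%. A noncentral t with 50 df gives 0.9998, consistent with the stated 99%. It bears on this point only through the arm size: one participant is 100/26 = 3.8 percentage points.

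**Checks by length of stay.** Post-dose checks per dosing day are 3 for a 4 h stay (45 min, 2 h, 4 h), 4 for 6 h, 5 for 8 h and 7 for 12 h. With three dosing days, a participant who always leaves at 4 h has 3 × 3 = 9 checks; one who always stays to 8 h has 3 × 5 = 15.

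**Assumptions.** The per-check crossing probability q is the same in every arm (no drug effect), from 1% to 10%. Checks are independent. The share kept late is 30% or 50% in a KAN-101 arm and 10% on placebo, and late stayers have k extra checks on d dosing days.

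**Formulas.** The chance of at least one crossing in m checks is p(m) = 1 − (1 − q)^m. The spurious excess is (share late on KAN-101 − share late on placebo) × [p(9 + kd) − p(9)].

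With k = 2 (stay to 8 h), all values in percent or percentage points:

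| q | p(9) | p(11) | p(15) | Excess, one day prolonged (30% / 50% late) | Excess, three days prolonged (30% / 50% late) |
|---|---|---|---|---|---|
| 1% | 8.6 | 10.5 | 14.0 | 0.36 / 0.73 | 1.07 / 2.14 |
| 2% | 16.6 | 19.9 | 26.1 | 0.66 / 1.32 | 1.90 / 3.81 |
| 5% | 37.0 | 43.1 | 53.7 | 1.23 / 2.46 | 3.34 / 6.68 |
| 10% | 61.3 | 68.6 | 79.4 | 1.47 / 2.94 | 3.63 / 7.26 |

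- One prolonged day with one or two extra checks: 0.2 to 2.9 points, or 0.05 to 0.8 participants of 26.
- Three prolonged days with two extra checks each: 1.1 to 7.3 points, or 0.3 to 1.9 participants of 26.
- Extreme case, a stay to 12 h on all three days (k = 4): 2.1 to 11.6 points, or 0.5 to 3.0 participants of 26.
- Equal shares kept late in both arms: zero.

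**Pre-dose readings.** SAP Part C 3.5.1 counts an AE as treatment-emergent from the treatment period start date, so pre-dose crossings on Days 4 and 7 also count. The shared core is then at least 9 + 2 = 11 checks. At q = 5% and 50% late on all three days, the excess becomes 0.4 × (0.95^11 − 0.95^17) = 0.4 × (0.569 − 0.418) = 6.0 points instead of 6.7.

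**Stays prolonged by orthostatic hypotension itself.** Such participants are already counted, so participant incidence does not change. Only an event count can rise. If each later crossing were entered as a new AE, two extra checks with 30% to 60% persistence would give 1 + 2 × 0.3 = 1.6 to 1 + 2 × 0.6 = 2.2 events per such participant.

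**After the fix.** Limited to 45 min, 2 h and 4 h on Days 1, 4 and 7, every participant who completes dosing has 9 checks in every arm, and the artefact from extra checks is zero for any q.

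**The case against.** The case against making much of this is substantial.

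- **The core is common.** A reader might infer that the whole series is uneven. It is not: inequality begins only after 4 h, and schedule and blinding are the same in all arms.
- **Many late readings cannot alter the participant count.** Only someone kept for a non-orthostatic reason, whose first crossing comes after 4 h, is added.
- **Repeats are undefined.** A reader might infer that every crossing becomes a separate Grade 3 AE. The text does not say whether repeats are one event or several.
- **Differential stay is inferred.** Protocol 2.2.3 also reports no Grade 3 TEAEs, no clinically relevant vital-sign trends and no meaningful safety differences among groups, and is silent on length of stay. Protocol 6.1.1 permits prophylactic medication before later infusions, and participants who stop dosing have fewer checks, which works in the opposite direction.
- **Independence is generous.** Readings within a person are likely correlated, which reduces the gain from extra checks; with perfect correlation it would be nil.
- **A late crossing may be real.** Orthostatic hypotension in someone kept for vomiting can be a true consequence of the reaction.
- **Listings exist.** SAP Part C 6.6 and Appendix 2.1 provide participant listings with all observations.

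All of this stands and limits the size and certainty of the point. It does not close the gap: neither document limits any by-arm comparison to shared post-dose times, and listings do not tabulate late readings by arm.

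**Conclusion.** The point holds as a gap in the analysis plan. Readings after 4 h depend on length of stay, a crossing is Grade 3 by rule, and the specified count takes no account of the number of readings. Unequal ascertainment between arms can therefore arise. A reader might go further and conclude that the arms are unequally ascertained, or that a KAN-101 excess would be false. The documents do not support either, since they give no stay, late share or crossing rate by arm and a late crossing may be genuine.

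Under the stated assumptions the artefact is about 0.2 to 3 points, under one participant of 26, if a single dosing day is prolonged. It is about 1 to 7 points, at most about two participants, if all three are prolonged to 8 h. Positive correlation between readings would lower these figures. The safety comparison is descriptive, without tests, and the IL-2 primary endpoint and its power are untouched. This is a modest improvement, worth making because it is cheap.

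**What to change.** In SAP Part C 6.6.1 and 6.6.3:

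1. Add a by-arm table of the number and percent of participants with a threshold crossing at the fixed post-dose readings (45 min, 2 h, 4 h), per dosing day and overall.
2. Give planned pre-dose crossings their own row, so that these shared readings are neither lost nor mixed with post-dose findings.
3. Show first crossings found only after 4 h, or only at event-triggered readings, in a separate row, with the number of readings per participant by arm.
4. State how repeat crossings in one participant are counted, both within a dosing day and across days.
5. Keep the all-readings TEAE table.

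The cost is SAP wording and one table from data already collected. Monitoring, discharge and care do not change. The downside is that the fixed-reading row omits genuine late events; these remain in the all-readings table and in the separate row.

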8.3.2.1. Oral Temperature and Respiratory Rate

For Parts A and B, oral temperature and respiratory rate will be assessed. Temperature and respiratory rate findings collected during the study will be considered source data and will not be required to be reported, unless otherwise noted.

For Part C, oral temperature and RR will be assessed and recorded in clinical database at timepoints described in the [SoA](#), ie,

- Approximately 5 minutes pre-dose;
- Approximately 45 minutes, 2 hours, and then, every 2 hours until discharge from the unit post dose.

Additionally, if a participant experiences treatment-emergent, clinically significant orthostatic hypotension or syncope, then, in addition to supportive care, temperature and RR will be collected every 2 hours, until discharge. **Note:** if planned assessments (pre-dose and 45 min, 2 hr and 4 hour post-dose) overlap unplanned assessments, temperature and RR will be measured only once, not twice at that time.

8.3.3. Electrocardiograms

A standard 12-lead ECG utilizing limb leads (with a 10-second rhythm strip) should be collected at screening using an ECG machine that automatically calculates the HR and measures PR interval, QT interval, QTcF, and QRS complex. Alternative lead placement methodology using torso leads (eg, Mason-Likar) should not be used given the potential risk of discrepancies with ECGs acquired using standard limb lead placement. The ECG should be performed prior to blood draws and after the participant has rested quietly for at least 5 minutes in a supine position. When collected, ECG values should be entered in clinical database.

Unscheduled ECGs are permitted per the investigator's discretion. In some cases, it may be appropriate to repeat abnormal ECGs to rule out improper lead placement as contributing to the ECG abnormality. If a machine-read QTc value is prolonged, as defined above, repeat measurements may not be necessary if a qualified medical provider's interpretation determines that the QTcF values are in the acceptable range.

ECG values of potential clinical concern are listed in [Appendix 8](#).

8.3.4. Clinical Safety Laboratory Assessments

Fasting at least 8 hours is required for the clinical safety laboratory tests. See [Appendix 2](#) for the list of clinical safety laboratory tests to be performed and the [SoA](#) for the timing and frequency. All protocol required- laboratory assessments, as defined in [Appendix 2](#), must be conducted in accordance with the laboratory manual and the [SoA](#). Unscheduled clinical laboratory measurements may be obtained at any time during the study to assess any perceived safety issues.

The Investigator must review the laboratory report, document this review, and record any clinically significant changes occurring during the study in the AE section of the CRF. Clinically significant abnormal laboratory test findings are those that are not associated with any underlying disease, unless judged by the investigator to be more severe than expected for the participant's condition.

All laboratory tests with values considered clinically significant and abnormal during participation in the study or within the follow-up period after the last dose of study intervention should be repeated until the values return to normal or baseline or are no longer considered clinically significant by the investigator or study medical monitor.

As part of amendment 3, if a participant experiences treatment-emergent, clinically significant orthostatic hypotension, syncope or treatment-related TEAE Grade 3 or above, then, in addition to supportive care, additional samples for safety laboratory tests (hematology, blood chemistry) will be collected.

If such values do not return to normal/baseline within a period of time judged reasonable by the investigator, the etiology should be identified and the sponsor notified.

See [Appendix 6](#) for suggested actions and follow-up assessments in the event of potential DILI.

See [Appendix 7](#) for instructions for laboratory testing to monitor kidney function and reporting laboratory test abnormalities.

8.3.4.1. Alternative Facilities for Clinical Safety Laboratory Assessment

Protocol-specified safety laboratory evaluations will be conducted at a central laboratory.

Non-protocol-specified laboratory evaluations as ordered by the investigator may be conducted at a local laboratory.

8.3.5. Physical Examinations

A complete physical examination will include, at a minimum, assessments of the cardiovascular, respiratory, gastrointestinal, and neurological systems. Height and weight will also be measured and recorded at screening only.

Investigators should pay special attention to clinical signs related to previous serious illnesses.

Physical examination findings collected during the study will be considered source data and will not be required to be reported, unless otherwise noted. Any untoward physical examination findings that are identified during the active collection period and meet the definition of an AE or SAE ([Appendix 3](#)) must be reported according to the processes in [Sections 8.4.1 to 8.4.3](#).

8.3.6. Pregnancy Testing

A serum pregnancy test is required at screening. Following screening, pregnancy tests may be urine or serum tests, and must have a sensitivity of at least 25 mIU/mL. Pregnancy tests will be performed in WOCBP at the times listed in the [SoA](#). Following a negative pregnancy test result at screening, appropriate contraception must be commenced and a second negative pregnancy test result will be required at the baseline visit prior to the participant's receiving the study intervention. Pregnancy tests will also be done whenever 1 menstrual cycle is missed during the active treatment period (or when potential pregnancy is otherwise suspected) and at the end of the study. Pregnancy tests may also be repeated if requested by IRBs/ECs or if required by local regulations. If a urine test cannot be confirmed as negative (eg, an ambiguous result), a serum pregnancy test is required. In such cases, the participant must be excluded if the serum pregnancy result is positive.

8.4. Adverse Events, Serious Adverse Events, and Other Safety Reporting

The definitions of an AE and an SAE can be found in [Appendix 3](#).

AEs may arise from symptoms or other complaints reported to the investigator by the participant (or, when appropriate, by a caregiver, surrogate, or the participant's legally authorized representative), or they may arise from clinical findings of the investigator or other healthcare providers (clinical signs, test results, etc).

The investigator and any qualified designees are responsible for detecting, documenting, and recording events that meet the definition of an AE or SAE and remain responsible to pursue and obtain adequate information both to determine the outcome and to assess whether the event meets the criteria for classification as an SAE or caused the participant to discontinue the study intervention (see [Section 7.1](#)).

During the active collection period as described in Section 8.4.1, each participant will be questioned about the occurrence of AEs in a nonleading manner.

In addition, the investigator may be requested by the sponsor to obtain specific follow -up information in an expedited fashion.

